1 BACKGROUND

Benzodiazepines ((z-)BZD) are prescribed worldwide extensively to treat anxiety and sleeping disorders, and used as adjuvant therapy in depression, pain management, and as muscle relaxants. Although it is recommended that treatment with (z-)BZD should be limited to only a few weeks and despite the fact that long-term-use is ineffective and also associated with adverse side effects, the prevalence of long-term use, which is most common for sleeping disorders, remains widespread. (Mugunthan 2011).

A recent systematic review summarizing current evidence-based discontinuation strategies indicate that gradual tapering of doses is an effective (z-)BZD discontinuation intervention for adult patients with long-term (z-)BZD use (CADH 2015).

Minimal interventions such as a discontinuation letter from a clinician or consultation with a general practitioner (GP) explaining both the risk of long-term (z-)BZD use and the advantages of discontinuation are effective in initiating the intervention process and achieving better (z-)BZD discontinuation outcomes when compared with usual care. Patients receiving such interventions are twice as likely to completely withdraw from (z-)BZD use (Mugunthan 2011).

Furthermore, a combination of tapering protocols with psychotherapy interventions result in superior discontinuation outcomes when compared to either individual strategy alone, and compared with alternative interventions such as medication review, consultation or education, and relaxation therapy (Paquin 2014, Gould 2014, Otto 2010).

Coupling a dose-tapering intervention with patient empowerment education improves the odds of (z-)BZD discontinuation significantly when compared with dose-tapering alone. Moreover, dose-tapering with structured education and follow-up visits, or written self-help instructions, result in higher (z-)BZD discontinuation rates than usual care (Tannenbaum 2014, Vicens 2014).

In summary, a combination of dose-tapering and non-pharmacological interventions such as psychotherapy interventions, self-help instructions and patient education produce better outcomes compared to stand-alone strategies.

Recently a small descriptive pilot study with a blended care approach combining an e-learning tool with face-to-face contacts for the discontinuation of (z-)BZD use for sleeping disorders in general practice was tested (Klaasen 2015). The results of this study suggest that a blended approach may be more effective than a minimal intervention such as a discontinuation letter or discontinuation advice and as effective as face-to-face interventions combining tapering protocols and education but need to be confirmed by a properly powered and controlled study.

These data prompted us to design a clustered randomized trial aiming to compare a blended approach with usual care for the discontinuation of chronic benzodiazepine use for a primary indication of sleeping disorders in adult patients in a primary care setting.

2 RATIONALE

(z-)BZD use is highly prevalent in Belgium. Each day 1.260.034 daily defined doses (DDD) of (z-)BZD are dispensed in Belgium. In 2013 up to 13% of the adult Belgian population had used (z-)BZD in the two weeks preceding the health interview survey (WIV-ISP. Gezondheidsenquête 2013) Half of the (z-)BZD users did so on a daily basis for at least 6 weeks (Anthierens 2012)). Women (20%) consumed more (z-)BZD than men (10%) and consumption rates increased with age mounting up to 35% in people aged 75 years and older (WIV-ISP. Gezondheidsenquête 2013). Belgium is the world's leader in terms of global consumption of (z-)BZD. In 2011 495 million DDD were sold in Belgium as compared to 180 million in the Netherlands. This despite the fact that in the past 15 years several campaigns have been organized in Belgium by the Federal Government. These included mass media campaigns and interventions targeting pharmacists and GPs in order to educate them and to provide them with aid to assist patients with questions regarding the use or discontinuation of (z-)BZD.

This high (z-)BZD consumption rate is problematic since (chronic) (mis-)use is associated with well-known complications which are more pronounced in older adults (Thomas 1998, Leipzig 1999, Glass 2005, Barker 2004, Billioti de Gage 2012, Belleville 2010, Kripke 2012, Soyka 2017). These include increased tolerance and addiction, disturbance of the physiological sleeping pattern, pharmacological interactions and interactions with alcohol use, increased risk of motor vehicle accidents, falls and hip fractures in the elderly, memory impairment, cognitive decline, depression and emotional blunting. More recently, (z-)BZD use has been associated with dementia and increased mortality (Kripke 2012, Soyka 2017, Zhong 2015, Takada 2016). These complications are jeopardising the personal health of (z-)BZD users and come along with substantial socio-economic costs.

The SOCOST study estimated the societal costs related to the use of addictive substances including alcohol, tobacco, illicit drugs and psychoactive pharmaceuticals in Belgium in 2012 (Vander Laenen 2012)). Direct and indirect costs of addictive substances were at 4,6 billion euros in Belgium (equivalent with 419 euros per capita or 1,19% of the Gross Domestic Product (GDP)) of which 5% or 215 million euros/year could be assigned to psychoactive medication. Also, premature mortality due to psychoactive medication was mainly caused by sedative-hypnotic drugs (52,4%) and methadone (33,8%). Finally, the study indicated psychoactive medication was responsible for as much as 1% of the total loss of 3,259,200 disability-adjusted life years (DALYs) in 2012. Although the SOCOST study was not able to provide drug specific data - especially related to the use of (z-)BZDs -, it's reasonable to conclude that (z-)BZD use is related to substantial direct and indirect societal costs and to loss of DALYs.

Taking into account the high prevalence of (z-)BZD misuse together with the health-related complications, the availability of non-drug alternatives for e.g. sleep disorders (Domus Medica 2005) and anxiety disorders (Trimbos Instituut 2013), and the socio-economic costs in Belgium, the development of a programme aiming to reduce (z-)BZD use would obviously be beneficial.

GPs have a pivotal role in the management of chronic (z-)BZD use. They are highly valued and trusted by their patients. Having a long-lasting relationship with one's GP makes the GP one of the best-placed persons to counsel and motivate the (z-)BZD-using patient to cease his chronic use. (z-)BZD users are highly dependent on prescriptions from their treating physicians in order to get their sedate-hypnotic products.

Nevertheless, GP's do not feel confident in managing the tapering and discontinuation of chronic (z-)BZD use, despite the availability of guidelines and tools such as "Anxiety, stress and sleeping problems. A toolbook for general practitioners" and "Sleeping pills and sedatives. How to assist your patients in the search for other solutions?" which were developed in 2005 and 2018, respectively by order of the Belgian Federal Government as part of a federal campaign for a responsible use of (z-)BZD (FOD Volksgezondheid 2005, [name] 2018). Moreover, as part of this campaign by the FOD Volksgezondheid, the guidelines were translated into training sessions for GPs, which discuss implementation in daily practice. These training sessions are ideal to be included in the context of a pragmatic trial, supporting usual care for benzodiazepines withdrawal in the GP practice. Nonetheless, GPs also perceive the management of (z-)BZD withdrawal as very time-consuming and nearly impossible to integrate into their patient care practices (Anthierens 2010).

With the growing use of internet, e-based approaches are becoming more popular. Among them, blended care, defined as a combination of care by applying an interactive educational e-tool in combination with face-to-face clinical consultations with the care provider, is a new and promising approach (Hards 2012, Wilhelmsen 2013). Blended care has already proven to be successful in treating sleeping disorders, supporting substance use disorders, in stress management for employees, treating depression and other psychiatric and somatic conditions (Kaldo 2015, Hermes 2016, Kawaguchi 2014, Ebert 2016, Andersson 2014).

A pilot study that was conducted recently in Belgium strongly suggested that blended care e.g. might also be an effective approach for the discontinuation of chronic (z-)BZD use (Klaasen 2015). In this study, the blended care intervention combined dose-tapering with (online) non-pharmacological interventions like self-help instructions and patient education, which has been shown to be more effective than a single strategy (CADH 2015). However, since patients go through the learning module on their own and at their own pace it is more feasible and less time-consuming for the GP and consequently easier to implement in general practice. Moreover, the availability of an e-tool may circumvent the lack of experience that poses an important barrier for GPs to engage in the management of (z-)BZD withdrawal. Finally, the standardised protocol-based e-tool in combination with face-to-face contact allows a tailor-made approach and is expected to enhance self-management of the patient (Wentzel 2016). Thus, a blended care approach may not only empower patients, but also facilitate and support GPs in the management of (z-)BZD withdrawal and hence result in better outcomes in terms of (z-)BZD discontinuation.

2.1 Assessment and management of risk

This clinical trial is a low risk intervention trial for the following reasons

- The use of the investigational e-tool is not associated with any risk for the patient
- The use of blended care in the treatment of mental health problems including addiction is supported by scientific evidence
- The additional diagnostic (toxicological screening) and monitoring (questionnaires) are not associated with an additional risk to the safety of the study participants and pose only a minimal burden as compared to normal clinical practice
- The prevalence and the severity of adverse events due to slow dose tapering of (z-)BZD is expected to be very low

Adverse events e.g. withdrawal symptoms are documented during the trial (see 3.6 Exploratory endpoints) and can usually be managed by the attending GP.

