3.6 Exploratory endpoints

- Self-reported changes in alcohol intake or other psychoactive substances.
- Severity of (z-)BZD dependency .
- Quality of sleep.
- Occurrence of withdrawal symptoms, patient-reported adverse effects and falls.
- Use of medical services.
- (z-)BZD-related interventions by GP other than prescriptions
- Visits to and interactions with the e-learning module.
- Patient's satisfaction
- Physician's satisfaction

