7.6 Baseline data

At study entry, the following baseline data will be collected for each participating patient:

- Demographics, comorbidities and medication
- Toxicological screening of urine
- Self-reported use of (z-)BZD (drug name(s), quantity)
- (z-)BZD prescriptions in last 6 months (drug name(s), quantity)
- Audit-C
- EQ5D-3L
- Benzodiazepine Dependence Self-Report Questionnaire
- Insomnia Severity Index
- HLS-EU-Q16

Except for the toxicological screening for which the procedure is explained in 7.7, data will be collected either by completion of the eCRF or via questionnaires sent to the patient.

The invitation to complete the first questionnaire will be sent after signature of the Informed Consent Form (ICF) and registration of the patient in the online platform Slaapzorgeloos/Dormir Sereinement. This first (baseline) questionnaire should thus be completed before the baseline visit takes place. By doing so, we would like to prevent that the patients' answers are influenced by the outcome of the randomisation (see section 7.3.1 *method of implementing the allocation sequence*).

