7.7 Trial assessments

Within the week following the enrolment of the 10th patient by the GP(s), the general practice will be allocated to either the blended care or usual care arm.

During the baseline visit, which will take place within 12 weeks after the screening visit, the GP will start the intervention, which will be either usual care or blended care for the discontinuation of benzodiazepines.

Assessment by GP

After the baseline visit, appointments –minimal 1- for follow-up and prescription renewals will be scheduled left at the discretion of the GP and depending on the needs of the patient until the end of dose reduction. In addition to these scheduled appointments, patients will be allowed to request an extra appointment with their GP when needed. This approach maximally reflects daily practice as should be in a pragmatic trial. The GPs will be asked to note in the Electronic Health Record (EHR) at each contact with the patient the (z-)BZD-related interventions delivered to the patients via standardized entry fields, and to document this data in the eCRF.

These interventions may include:

- Advise to discontinue (z-)benzodiazepines
- Discussion of tapering schedule
- Discussion of withdrawal symptoms
- Discussion of sleep quality

- Discussion of coping strategies, triggers and facilitators
- Decrease of benzodiazepine dose
- Increase of benzodiazepine dose

In the exceptional circumstances of COVID-19, EC Research allows the PI or his delegate to use telemedicine visits. This means that the GP can perform a consultation by telephone or video conference. As with regular consultations, all (z-)BZD interventions need to be documented in the EHR and eCRF of the patient.

E-questionnaires

Patients will be requested to complete the following e-questionnaires at weeks 6, 12, 26 and 52 comprising of the validated EQ5D-3L, Audit-C and Insomnia Severity Index. Furthermore, the e-questionnaire will include questions about self-reported use of (z-)BZD and other psychoactive medication, self-reported falls and use of medical services in the past period.

The questionnaires will be e-mailed to the study participants at week 5, 11, 25 and 51 with the request to complete them within 2 weeks. A reminder will be sent after 1 week to all participants who have not responded yet and every week after until response or the deadline

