9 SAFETY REPORTING

The risk of adverse events occurring as a consequence of the intervention in this trial is unlikely therefore safety reporting will be limited to the safety reporting that is necessary in routine care (https://www.fagg-afmps.be/nl/notification_effets/humane_geneesmiddelenbewaking/melding_gezondheidszorgbeoefenaars).

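### Withdrawal symptoms, patient-reported adverse effects and dependence severity are exploratory endpoints, but the text of section 7.7 lists no follow-up item that records them

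*Combined protocol and SAP*

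**What the plan says.** Section 2.1 gives four bulleted reasons for calling the trial low risk. A separate sentence then says how harms will be observed: "Adverse events e.g. withdrawal symptoms are documented during the trial (see 3.6 Exploratory endpoints"). Section 3.6 names "Occurrence of withdrawal symptoms, patient-reported adverse effects and falls" as one exploratory endpoint and severity of (z-)BZD dependence as another. It attaches no instrument, definition or time point to either.

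The collection of follow-up data is described in 7.7:

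- **E-questionnaires at weeks 6, 12, 26 and 52**, "comprising of the validated EQ5D-3L, Audit-C and Insomnia Severity Index", together with "questions about self-reported use of (z-)BZD and other psychoactive medication, self-reported falls and use of medical services in the past period".
- **GP entries at each contact**, which record the interventions delivered. One of the example entries is "Discussion of withdrawal symptoms". At least one follow-up appointment is required; beyond that, timing is left to the GP and the patient's needs.

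The "Benzodiazepine Dependence Self-Report Questionnaire" appears in the baseline list in 7.6 and is not named again in 7.7. Section 9 states that "safety reporting will be limited to the safety reporting that is necessary in routine care". Section 10.3 sets out no analysis for any exploratory endpoint.

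**The concern.** The trial encourages about 1200 daily users to reduce and stop, and it is designed to detect a rise in discontinuation from 15% to 25% (section 10.1). If the intervention works as hoped, more patients in the blended-care arm will go through a taper. Withdrawal symptoms are then an outcome on which the arms could plausibly differ, and readers will want to set them beside the gain in discontinuation. Section 2.1 also expects adverse events from slow tapering to be rare and mild. Data collected in the same way in both arms would let that expectation be checked.

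The follow-up schedule in the text does not supply such data. What is not asked at weeks 6 to 52 cannot be recovered at the analysis stage.

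**Working it through.** No figure in the plan is in dispute and no calculation is needed. The check is to take each component of the relevant 3.6 endpoints and look for a listed source after baseline.

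| Component in 3.6 | Follow-up source in the text | Time points out of 4 |
|---|---|---|
| Falls | e-questionnaire ("self-reported falls and use of medical services in the past period") | 4 |
| Use of medical services | e-questionnaire | 4 |
| Quality of sleep | Insomnia Severity Index | 4 |
| Alcohol and other psychoactive substances | Audit-C and a question on other psychoactive medication | 4 |
| Occurrence of withdrawal symptoms | none | 0 |
| Patient-reported adverse effects | none | 0 |
| Severity of dependence | baseline questionnaire only | 0 |

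So the e-questionnaire list is detailed enough to supply several 3.6 items, including falls, which share a bullet with the two missing items.

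Next, could another source in the document fill the gap?

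1. **GP entries (7.7).** The entry on withdrawal symptoms records that a conversation took place. It does not record whether symptoms occurred, or their type, severity or date. Its frequency depends on how often patient and GP meet, which has no fixed schedule. GPs are unmasked after allocation (7.4), and the blended-care arm is built around discussing the patient's experiences (8.1). The count of discussions could therefore differ between arms even if symptoms did not.
2. **Safety reporting (section 9).** This is routine-care reporting only, so there is no trial-specific record of adverse events as a back-up.
3. **Nested interviews (7.10).** About 14 to 18 patients are purposively sampled. That cannot support a between-arm comparison.
4. **E-tool tracking (8.2).** This records use of the learning module, which belongs to the intervention arm.
5. **Urine screening (7.7).** This measures drug presence, not symptoms.

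None of the five gives the occurrence of withdrawal symptoms or adverse effects in both arms, and none gives a change in dependence score.

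**The case against.** Four points on the other side deserve weight.

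**The list may not be complete.** Figure 3, the flow chart of procedures in 7.8, could not be read in the copy reviewed. Section 7.7 says what the e-questionnaire will include and what GP interventions may include, and neither wording closes the list. It also names no source for patient or physician satisfaction, so the forms may hold more than the text shows. This stands. Absence can be asserted for the text of 7.6 and 7.7, not for the forms. Against it, 7.7 says the follow-up questionnaires are shorter than the baseline one, which fits the dependence scale being dropped after baseline.

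**Harms are not left unmeasured.** A reader might infer that the harms of dose reduction cannot be compared between arms at all. The documents do not support that. Falls, insomnia severity, quality of life, alcohol use, other psychoactive medication and service use are collected in both arms at four fixed times.

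**The low-risk classification does not depend on this.** A reader might also infer that it does, because the sentence sits in 2.1. The four bulleted reasons are separate from the sentence on documentation, and documentation is not one of them.

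**The GP record is a form of documentation.** Follow-up visits in both arms cover withdrawal-related problems, and contacts are noted in the health record and eCRF. The plan never proposes the discussion entry as a measure of occurrence, so it cannot be faulted for misusing it. That is fair, but 3.6 names occurrence as the endpoint, and the discussion entry does not measure it.

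**Conclusion.** The point holds for three exploratory endpoints: occurrence of withdrawal symptoms, patient-reported adverse effects and severity of dependence. In the text, each has a follow-up source at 0 of 4 planned time points. Dependence severity is measured once, at baseline, so change cannot be estimated. Following 7.7 as written would leave these endpoints without unbiased between-arm data.

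This goes beyond missing detail, because the data could not be recovered later and the remedy is cheap. It does not touch the primary analysis, the risk classification in 2.1, or the comparison of the other harms and patient-reported outcomes that 7.7 does collect. The conclusion assumes that Figure 3 and the forms add nothing to the text of 7.6 and 7.7. If they do, what remains is an inconsistency in 7.7 to correct.

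**What to change.** If Figure 3 or the e-forms already contain these items, name them in 7.7 with their time points. Otherwise:

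- In 7.7, add a short closed checklist on withdrawal symptoms and adverse effects to the existing e-questionnaires at weeks 6, 12, 26 and 52. Give it a recall period covering the interval since the last questionnaire, as is done for falls, so that a taper between two time points is not missed.
- Repeat the baseline dependence questionnaire at one or more follow-up points, for example week 52.
- In 10.3, state that these endpoints will be reported descriptively by arm, with intervals that allow for clustering.

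The cost is a protocol amendment, a few added questions on a platform that already has time points and reminders, and slightly longer follow-up questionnaires. Section 7.7 puts the baseline set at fewer than 50 questions and the follow-up sets below that. Patients will still be unmasked when they answer, so some reporting bias remains possible. Fixed questions at fixed times do remove the dependence on how often each arm sees the GP.

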3 OBJECTIVES AND ENDPOINTS / OUTCOME MEASURES

3.1 Primary objective

The primary aim of this trial is to compare the effect of blended care combining an interactive educational e-tool with face-to-face clinical consultations versus usual care on the proportion of subjects that has discontinued (z-)BZD use 12 months after start of the intervention in a population of adult primary care patients chronically using (z-)BZD for a primary indication of sleeping disorders.

Null hypothesis: blended care is not superior to usual care in terms of the proportion that has discontinued (z-)BZD use 12 months after start of the intervention.

Alternative hypothesis: blended care will increase the proportion of subjects that has discontinued (z-)BZD use 12 months after initiation of the intervention compared to usual care.

PICOT

Population:	Patients aged 18 and older receiving prescriptions for (z-)BZD use on a daily basis in the last 6 months for a primary indication of sleeping problems.
Intervention	Blended care combining an interactive educational e-tool with face-to-face clinical consultations with the GP.
Comparator	Care as usual for chronic (z-)BZD use left at the discretion of the GP. This may include a minimal intervention (discontinuation letter or discontinuation advice) or a more extended intervention, in combination with (z-)BZD tapering.
Outcome	The proportion of patients that discontinued (z-)BZD at 12-months assessed by toxicological screening for (z-)BZD in urine.
Time	The outcome will be assessed 12 months after initiation of the intervention.

